5.1 Primary outcomes

The primary outcomes of this study measure the respective primary objectives stated in section 2.1.

- i. Estimate the number of eligible patients in Group A (step-up) and Group B (step-down)
- ii. Examine the acceptability of using a mixed model of consent (prospective and deferred), i.e. estimate the number of prospective and deferred consent among the treatment groups
- iii. Assess the feasibility of randomising at least 50% of eligible patients, i.e. examine if 50% of the eligible patients were randomised into the trial
- iv. Test the practical aspects of implementing the study protocol in terms of initiation, maintenance and weaning of the study intervention, i.e. estimate:
 - a. Initiation
 - Proportion receiving allocated treatment
 - Time from randomisation to initiation
 - b. Maintenance (excluding patients who did not continue treatment for the full six hours)
 - Proportion at correct pressure/flow rate by Hour 2
 - Proportion with >50% of time at correct pressure/flow rate in first 6 hours
 - c. Weaning
 - Proportion started weaning when should (by next time point)
 - Proportion weaned by prescribed flow rate (HFNC) or pressure (CPAP) according to protocol
- v. Assess whether a modified COMFORT score (COMFORT score minus the respiratory component) can be used to measure patient tolerance to CPAP/HFNC, i.e. estimate:
 - a. Number of completed COMFORT scores
 - b. Number of lower COMFORT scores when not tolerating (within/between patients)

- vi. Assess the feasibility of using the Parental Stressor Scale: PICU (PSS:PPICU) to measure parental stress 24 hours after the initiation of CPAP/HFNC, i.e. estimate:
 - b. Number of questionnaires returned
 - c. Number/quality of questionnaires completed

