5.2 Secondary outcomes

The secondary outcomes of this study measure the respective secondary objectives stated in section 2.2.

- i. To determine the rate of intubation - i.e. estimate the proportion of children randomised to the intervention or control who need intubation (Group A) or re-intubation (Group B) within 72 hours of randomisation
- ii. To determine the rate of treatment failure - i.e. estimate the proportion of children randomised to the intervention or control who fail the assigned treatment and require either crossover or escalation to other forms of ventilation within 72 hours of randomisation
- iii. To assess safety – i.e. estimate the number of children who experience pre-specified adverse events i.e.
 - a. Pneumothorax
 - b. Pneumomediastinum
 - c. Subcutaneous emphysema
 - d. Abdominal distension
 - e. Nasal or facial trauma
 - f. Facial trauma
 - g. Facial thermal injury
 - h. Respiratory/Cardiac arrest
 - i. Aspirationduring the period they were receiving non-invasive respiratory support
- iv. To assess physiological effects – i.e. estimate changes in:
 - a. oxygenation
 - b. pCO₂ levels

- c. heart rate
 - d. respiratory rate
 - e. and work of breathing
- in the first 24 hours after the initiation of CPAP/HFNC
- v. To assess effects on patient outcome – i.e. estimate:
 - a. length of PICU stay
 - b. hospital stay
 - c. length of invasive ventilation
 - d. length of non-invasive support
 - e. ventilator-free days at day 28
 - f. PICU mortality
 - g. hospital mortality

6. Power calculation

Since this is a feasibility study, no formal sample size calculations was performed. Based on analysis of audit data, we expect around 250 eligible patients over the 6-month period at the three sites. Assuming a 50% recruitment rate, we will have recruited 120 study patients (around 40 patients in Group A). Data from the literature suggests a 20% rate of intubation for Group A (i.e. we expect to see eight intubation events), and a 10% rate of re-intubation for Group B (i.e. we expect to see eight re-intubation events).

7. Statistical methods

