- iii. Mean (SD) modified COMFORT score at individual time points by tolerating allocated treatment (Yes or No) at that time point
- iv. Mean (SD) across patients of the mean within-patient modified COMFORT score for patients with a highest level of respiratory distress of moderate or severe compared with those with a highest level of none or mild

Assessment of the suitability of the PSS:PICU will be evaluated by:

- i. Number and percentage of parents returning a completed questionnaire
- ii. Number and percentage of returned questionnaires with:
 - a. All questions completed
 - b. >90% of questions completed

The number and percentage of patients experiencing treatment failures, defined as crossover or escalation to other forms of ventilation within 72 hours of randomisation, will be reported for each group. Breakdowns of the numbers of crossovers and escalation (by level of respiratory support) will be reported.

The number and percentage of patients experiencing each pre-specified adverse event (plus any other adverse events as reported) will be summarised for each treatment group. Numbers of severe adverse events and their reported relatedness to treatment will be reported in text.

The physiological effects of treatment will be presented graphically by plotting the mean \pm SD of each physiological parameter at the time points recorded (Hours 0, 1, 2, 3, 4, 5, 6, 12, 24, 36, 48 and 72).

A comparison of outcomes by treatment group will be reported for the following outcome measures:

- i. Intubation within 72 hours
- ii. Treatment failure within 72 hours (separately for crossover and escalation patients)
- iii. Length of PICU stay
- iv. Length of hospital stay
- v. Length of invasive ventilation
- vi. Length of non-invasive support
- vii. Ventilator-free days at day 28
- viii. PICU mortality
- ix. Hospital mortality

Binary outcomes will be reported as the number and percentage in each group, the risk ratio and absolute risk reduction with 95% confidence intervals. Continuous outcomes will be reported as the mean (SD) and median (IQR) in each group and the difference in means with 95% confidence interval.

Differences in treatment effect between Group A and Group B for all outcome measures will be tested as interaction tests (Mantel-Haenszel tests for binary outcomes, interaction terms in linear regression models for continuous outcomes) and presented as forest plots.

9. Reporting conventions

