Work of breathing					
Respiratory distress, n (%)					
	None	XX (XX.X)	XX (XX.X)	XX (XX.X)	XX (XX.X)
	Mild	XX (XX.X)	XX (XX.X)	XX (XX.X)	XX (XX.X)
	Moderate	XX (XX.X)	XX (XX.X)	XX (XX.X)	XX (XX.X)
	Severe	XX (XX.X)	XX (XX.X)	XX (XX.X)	XX (XX.X)

n: Number of patients; %: Percentage of patients; N: Total number of patients;
SD: Standard deviation; IQR: Inter-quartile range

Table 3: Adherence by treatment groups

Variables		HFNC	CPAP
		N = XXX	N = XXX
Initiation:			
Randomised treatment started, n/N (%)			
Group A		XX/XX (XX.X)	XX/XX (XX.X)
Group B		XX/XX (XX.X)	XX/XX (XX.X)
Total		XX/XX (XX.X)	XX/XX (XX.X)
Time from randomisation to initiation (hours)			
Mean (SD)			
Group A		XX.X (XX.X)	XX.X (XX.X)
Group B:			
Planned		XX.X (XX.X)	XX.X (XX.X)
Rescued		XX.X (XX.X)	XX.X (XX.X)
Total		XX.X (XX.X)	XX.X (XX.X)
Median (IQR)			
Group A		XX (XX,XX)	XX (XX,XX)
Group B:			
Planned		XX (XX,XX)	XX (XX,XX)
Rescued		XX (XX,XX)	XX (XX,XX)
Total		XX (XX,XX)	XX (XX,XX)
Maintenance:			
At correct pressure/flow rate by Hour 2, n/N (%)			
Group A		XX/XX (XX.X)	XX/XX (XX.X)
Group B		XX/XX (XX.X)	XX/XX (XX.X)
Total		XX/XX (XX.X)	XX/XX (XX.X)
Treated >50% of time at correct pressure/flow rate in first 6 hours, n/N (%)			
Group A		XX/XX (XX.X)	XX/XX (XX.X)
Group B		XX/XX (XX.X)	XX/XX (XX.X)
Total		XX/XX (XX.X)	XX/XX (XX.X)
Weaning:			
Proportion started weaning in whom FiO ₂ was <0.40, n/N (%)			
Group A		XX/XX (XX.X)	XX/XX (XX.X)
Group B		XX/XX (XX.X)	XX/XX (XX.X)
Total		XX/XX (XX.X)	XX/XX (XX.X)
Proportion weaned by correct amount, n/N (%)			
Group A		XX/XX (XX.X)	XX/XX (XX.X)
Group B		XX/XX (XX.X)	XX/XX (XX.X)
Total		XX/XX (XX.X)	XX/XX (XX.X)

n: Number of patients; %: Percentage of patients; N: Total number of patients;
SD: Standard deviation; IQR: Inter-quartile range

Table 4: Modified COMFORT score and PSS:PICU by treatment group

Variables	HFNC	CPAP
	N = XXX	N = XXX
Modified COMFORT score:		
Modified COMFORT score completed, n/N (% of all eligible time points)		
Group A	XX (XX.X)	XX (XX.X)
Group B	XX (XX.X)	XX (XX.X)
Total	XX (XX.X)	XX (XX.X)
Patients with at least one modified COMFORT score completed, n/N (%)		
Group A	XX (XX.X)	XX (XX.X)
Group B	XX (XX.X)	XX (XX.X)
Total	XX (XX.X)	XX (XX.X)
Modified COMFORT score (Hour 1-6) by tolerating randomised treatment at individual time points, mean (SD) [N]		
Group A		
Yes	XX.X (XX.X) [XX]	XX.X (XX.X) [XX]
No	XX.X (XX.X) [XX]	XX.X (XX.X) [XX]
Group B		
Yes	XX.X (XX.X) [XX]	XX.X (XX.X) [XX]

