No	XX.X (XX.X) [XX]	XX.X (XX.X) [XX]
Mean modified COMFORT score (Hour 1-6) by patient's highest level of respiratory distress, mean (SD) [N]		
Group A		
None/Mild	XX.X (XX.X) [XX]	XX.X (XX.X) [XX]
Moderate/Severe	XX.X (XX.X) [XX]	XX.X (XX.X) [XX]
Group B		
None/Mild	XX.X (XX.X) [XX]	XX.X (XX.X) [XX]
Moderate/Severe	XX.X (XX.X) [XX]	XX.X (XX.X) [XX]
Use of sedative agents, n (%):		
Group A	XX (XX.X)	XX (XX.X)
Group B	XX (XX.X)	XX (XX.X)
Total	XX (XX.X)	XX (XX.X)
PSS:PICU:		
PSS:PICU questionnaire returned, n/N (%)		
Group A	XX (XX.X)	XX (XX.X)
Group B	XX (XX.X)	XX (XX.X)
Total	XX (XX.X)	XX (XX.X)
PSS:PICU questionnaire 100% complete, n/N (%)		
Group A	XX (XX.X)	XX (XX.X)
Group B	XX (XX.X)	XX (XX.X)
Total	XX (XX.X)	XX (XX.X)
PSS:PICU questionnaire >90% complete, n/N (%)		
Group A	XX (XX.X)	XX (XX.X)

	Group B	XX (XX.X)	XX (XX.X)
	Total	XX (XX.X)	XX (XX.X)
PSS:PICU	Group A:		
	Mean (SD)	XX.X (XX.X)	XX.X (XX.X)
	Median (IQR)	XX (XX,XX)	XX (XX,XX)
	Group B:		
	Mean (SD)	XX.X (XX.X)	XX.X (XX.X)
	Median (IQR)	XX (XX,XX)	XX (XX,XX)

n: Number of patients; %: Percentage of patients; N: Total number of patients;
SD: Standard deviation

Table 5: Treatment failure by treatment group

Variables	HFNC	CPAP
	N = XXX	N = XXX
Treatment failure:		
Crossover or escalation to other forms of ventilation within 72 hours of randomisation, n/N (%)		
Group A	XX/XX (XX.X)	XX/XX (XX.X)
Group B	XX/XX (XX.X)	XX/XX (XX.X)
Total	XX/XX (XX.X)	XX/XX (XX.X)
Crossover:		
Crossover from HFNC to CPAP or CPAP to HFNC, n/N (%)		
Group A	XX/XX (XX.X)	XX/XX (XX.X)
Group B	XX/XX (XX.X)	XX/XX (XX.X)
Total	XX/XX (XX.X)	XX/XX (XX.X)
Treatment escalation:		
Intubation and ventilation, n/N (%)		
Group A	XX/XX (XX.X)	XX/XX (XX.X)
Group B	XX/XX (XX.X)	XX/XX (XX.X)
Total	XX/XX (XX.X)	XX/XX (XX.X)
Non-invasive CPAP/PS, n/N (%)		
Group A	XX/XX (XX.X)	XX/XX (XX.X)
Group B	XX/XX (XX.X)	XX/XX (XX.X)
Total	XX/XX (XX.X)	XX/XX (XX.X)
Non-invasive BiPAP, n/N (%)		
Group A	XX/XX (XX.X)	XX/XX (XX.X)
Group B	XX/XX (XX.X)	XX/XX (XX.X)
Total	XX/XX (XX.X)	XX/XX (XX.X)
Other, n/N (%)		
Group A	XX/XX (XX.X)	XX/XX (XX.X)
Group B	XX/XX (XX.X)	XX/XX (XX.X)
Total	XX/XX (XX.X)	XX/XX (XX.X)

n: Number of patients; %: Percentage of patients; N: Total number of patients

Table 6: Adverse events by treatment group

Variables		HFNC	CPAP
		N = XXX	N = XXX
Safety - Adverse events			
Pneumothorax, n (%)			
	Group A	XX (XX.X)	XX (XX.X)
	Group B	XX (XX.X)	XX (XX.X)
	Total	XX (XX.X)	XX (XX.X)
Pneumomediastinum, n (%)			

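### Table 4 gives the two modified COMFORT score contrasts only within four arm-by-group strata, with no overall estimate, although SAP Section 8 states both unsplit

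*SAP*

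**What the plan says.** Section 5.1, item v, sets the question: "Assess whether a modified COMFORT score (COMFORT score minus the respiratory component) can be used to measure patient tolerance to CPAP/HFNC". It has two limbs: how many scores were completed, and whether scores are lower when a child is not tolerating support, looked at both within and between patients.

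Section 8 lists four items for judging the score. Two concern completion. The other two are the score contrasts. Item iii is "Mean (SD) modified COMFORT score at individual time points by tolerating allocated treatment (Yes or No) at that time point". Item iv averages each child's scores and compares children whose worst distress was moderate or severe with those whose worst was none or mild. Neither item mentions a split by treatment arm or by Group A/B.

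Table 4 in Section 10 lays both contrasts out under separate HFNC and CPAP columns, with separate Group A and Group B rows: "Modified COMFORT score (Hour 1-6) by tolerating randomised treatment at individual time points, mean (SD) [N"] and, for distress, "highest level of respiratory distress, mean (SD) [N"]. That makes four strata and eight cells per contrast. Neither contrast has a Total row or a both-arms column. The COMFORT completion rows, the sedation row and the PSS:PICU return and completeness rows do have a Total, one per arm.

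Section 8 plans differences with 95% confidence intervals only for its list of outcome comparisons by arm (the Table 7 outcomes). The COMFORT contrasts are not on that list.

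**The concern.** Whether a score separates children who tolerate support from those who do not is a question about the instrument, and all children in both arms inform it. Table 4 instead presents it as four separate small comparisons, each without a difference or an interval. The reader must combine four pairs of means by eye, and these can differ in direction by chance alone. A score that does follow tolerance could look inconsistent and be dropped for the full trial, or one favourable stratum could be over-read. Judging the score's suitability is one of the trial's primary objectives, so the display matters.

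**Working it through.** **Sizes from the plan.** Section 6 gives "120 study patients (around 40 patients in Group A"), so about 80 in Group B. The total comes from "we expect around 250 eligible patients over the 6-month period" and "Assuming a 50% recruitment rate": 250 × 0.50 = 125, against the stated 120. The gap of 5 is consistent with rounding (120 would need 240 eligible, or a 48% rate) and does not affect this point. The plan's event counts reproduce: 40 × 20% = 8 and 80 × 10% = 8. The plan states no precision figure for COMFORT to reproduce.

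**Assumptions not in the SAP.** Equal arms, complete data, a common SD, and 20%, 30% or 50% of children in the moderate/severe class. The strata are then 20 and 20 children (Group A) and 40 and 40 (Group B).

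**Distress contrast (one mean per child).** Half-width in SD units = t(0.975, n1+n2−2) × √(1/n1 + 1/n2).

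Worked at a 30% share:
- Group A stratum, 6 v 14: 2.101 × √(1/6 + 1/14) = 2.101 × 0.488 = 1.03.
- Group B stratum, 12 v 28: 2.024 × √(1/12 + 1/28) = 2.024 × 0.345 = 0.70.
- All children, 36 v 84: 1.980 × √(1/36 + 1/84) = 1.980 × 0.199 = 0.39.

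| Moderate/severe share | Group A stratum | Group B stratum | Pooled |
|---|---|---|---|
| 20% | 1.17 (4 v 16) | 0.80 (8 v 32) | 0.45 (24 v 96) |
| 30% | 1.03 (6 v 14) | 0.70 (12 v 28) | 0.39 (36 v 84) |
| 50% | 0.94 (10 v 10) | 0.64 (20 v 20) | 0.36 (60 v 60) |

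An estimate stratified on the four strata has the same pooled half-widths to two decimals, so adjusting for arm and group costs almost nothing here. The stratum interval is about 2.6 times (Group A) and 1.8 times (Group B) as wide as the pooled one. For a given share, that ratio depends on the stratum sizes and not on any assumed COMFORT SD.

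**Consistency of direction.** This assumes, for illustration only, a true difference of 0.5 SD. At a 30% share the chance of a wrong-way result is Φ(−0.5/0.488) = 0.153 in a Group A stratum and Φ(−0.5/0.345) = 0.074 in a Group B stratum. The chance that at least one of the four points the wrong way is 1 − (0.847² × 0.926²) = 0.38. It is 0.47 at a 20% share and 0.33 at 50%.

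**Tolerance contrast (one score per time point, Hours 1-6).** There are up to 6 × 20 = 120 scores per Group A stratum, 6 × 40 = 240 per Group B stratum and 6 × 120 = 720 overall, correlated within child. With observations divided by 1 + 5 × ICC, the half-width is 1.96 × √[(1 + 5 × ICC)/(6n) × (1/p + 1/(1−p))], where n is the number of children and p the share of scores not tolerating.

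| p | ICC | Group A stratum | Group B stratum | Pooled |
|---|---|---|---|---|
| 25% | 0.3 to 0.7 | 0.65-0.88 | 0.46-0.62 | 0.27-0.36 |
| 10% | 0.3 to 0.7 | 0.94-1.27 | 0.67-0.89 | 0.38-0.52 |

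Both p and the ICC are assumptions. This design effect treats tolerance as fixed within a child. Where children change status, the within-child comparison would be more precise, which is a reason to model the time-point scores.

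**The case against.** Several objections have force.

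- **The text already covers the overall contrast.** Section 8 states both items unsplit, and Section 10 is only a set of proposed shells. This stands: the fault is a table narrower than its text, and pooling is not ruled out. But Section 8 plans no difference or interval for either contrast.
- **A reader could pool the cells.** For the distress contrast this is right, because mean, SD and N per cell suffice. For the tolerance contrast the pooled mean is recoverable but a valid interval is not, since the table carries nothing on correlation within child.
- **The plan is descriptive.** Section 6 says "Since this is a feasibility study, no formal sample size calculations was performed". This stands against using power as a yardstick, and none is used here. It does not argue for the less precise of two available descriptions.
- **Splitting by group is sensible.** Group A can enter on moderate distress, while planned Group B children enter whatever their condition. Crude pooled means could therefore mix the contrast with Group A versus B. This stands, and is why the overall estimate must be adjusted.
- **Other rows lack a Total too.** The PSS:PICU score rows have none, and the Totals that exist are per arm. This is true, but does not affect the point.

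A reader might infer that primary outcome v as a whole is judged on these cells, or that they are too small to answer it. The documents support neither. Outcome v also has a completion limb with Total rows per arm, and no rule ties the suitability conclusion to the split cells. The SAP gives no COMFORT SD, target difference or class share from which inadequacy could be shown. In the tolerance contrast the counts are time points and need not be small.

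**Conclusion.** The point holds as a mismatch between Table 4 and Section 8 items iii-iv that costs precision on the score-versus-tolerance limb of primary outcome v. With equal arms and a 20-50% moderate/severe share, the distress contrast has a 95% CI half-width of about 0.94-1.17 SD per Group A stratum and 0.64-0.80 SD per Group B stratum, against 0.36-0.45 SD pooled. The tolerance contrast loses precision in a similar proportion, with absolute widths that depend on the assumed ICC and share not tolerating. The shares and ICC are assumed, so the widths are ranges and not predictions. It is worth correcting because no new data are needed, but it does not show that the question cannot be answered.

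**What to change.** Add to Table 4, for each of the two contrasts, one overall mean difference with its 95% CI, pooled over arms and groups and adjusted for arm and Group A/B.

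- **Distress contrast:** use one mean per child.
- **Tolerance contrast:** keep the time-point scores and use a patient random effect or patient-clustered standard errors. One mean per child would not work here, because a child can be tolerating at one time point and not at another. Averaging would discard the within-patient comparison that outcome v names.

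Add a matching sentence to Section 8, stating that the score-versus-tolerance conclusion rests on these overall estimates. Keep the existing arm-by-group cells as a consistency display.

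The cost is two estimates from data already planned for collection. The small downside is that an overall figure assumes the score behaves similarly across arms and groups. The retained cells let the reader check that.
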